6.1.8 Efficacy Data with High Doses of Steroids Use and Rescue Medications Use

Corticosteroids Use:

A subject may use corticosteroids or increased dose levels of corticosteroids for reasons other than CD, and may start corticosteroid tapering at 8 weeks. If the subject experiences a worsening of disease activity during the taper, and/or the oral corticosteroid dose temporarily increased, in these circumstances the subject will be considered a treatment failure in the steroid free remission analysis but will continue to remain on the study and complete all scheduled visits.

Use of Rescue Medications:

Final Version 3.0, 05 April 2018

Subjects rescued with the following treatments or whose baseline doses/regimens are increased to treat new or unresolved CD symptoms may remain on the study drug at the discretion of the investigator and continue to be assessed at all scheduled study visits:

- Oral or rectal 5-ASA compounds
- Azathioprine or 6-mercaptopurine (6-MP) or methotrexate
- Antibiotics as treatment of CD
- Total parenteral nutrition as treatment of CD
- Systemic or rectal corticosteroid therapy
- Anti-TNF or other biologic agent

In the ITT efficacy analyses, subjects who initiate or modify dose/regimens to treat CD symptoms will be considered as treatment failures.

6.1.9 Determination of Sample Size

The sample size justification is provided in the protocol and was based on the review of published literature in similar patient population (Sandborn et al., 2013). A total sample size of 410 subjects (205 per treatment arm) was computed to be sufficient with one stratification anti-TNF agent use (yes/no) to detect a minimum difference of 15 percentage points between RHB-104 treatment (36% Remission) and Placebo (21% Remission) with 90% Power at two-sided significance level, $\alpha=0.05$. The test statistic used for this analysis was a two-sided Cochran-Mantel-Haenszel (CMH) test controlling for the stratification variable (anti-TNF agents (yes/no) under the ITT principle. These calculations were made to allow for two sequential tests to be made using the O'Brien-Fleming spending function to determine the test boundaries. The interim analysis (first sequential test) will occur when 50% of the patients have their outcome data measured (i.e., reach 26 weeks of follow-up). The 2-sided alpha level for stopping the trial for efficacy at the interim analysis is 0.003. If this criterion is not met the trial will be continued and the final analysis (second sequential test) will be performed using a 2-sided alpha level of 0.049 for testing the primary outcome (Elashoff, 2007). In all analyses, subjects with missing 26 week assessments will be assumed to not be in a state of remission at 26 weeks.

It should be noted that the intervention effect used in the sample size derivation for the study is 15% improvement in 26 week remission success, however a clinically meaningful difference in this measure (26 week remission success proportion) is 9% (in absolute percent) based on clinical expert opinion. Therefore, any statistically significant difference between groups that has an observed percent difference of 9% or larger would indicate that treatment is effective.

Protocol Version 11.0 curtails the number of expected enrolled patients to 324 (162 per group). Final analysis of the data is to be carried out when approximately 324 patients have completed the Week 26 primary endpoint assessment. This sample size curtailment reflects the study's current accrual trends. The anticipated power will be at least 80% given the study design stage assumptions regarding the treatment groups primary efficacy endpoint (36% RHB-104 vs. 21% Placebo).

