2.2.2 Key Secondary Efficacy Endpoints/Variables

Key Secondary efficacy endpoints include the following:

- Proportion of subjects experienced response at week 26, where response is defined as reduction from baseline of ≥ 100 in CDAI score. Subjects who have a change from baseline to week 26 in CDAI score which is not a reduction of ≥ 100 or who do not have a change from baseline to week 26 in CDAI score will be classified as not experienced response.
- Proportion of subjects in remission Week 52, where remission is defined as a subject having a CDAI score of < 150 . Subjects who have a week 52 CDAI measurement ≥ 150 or who do not have a CDAI measurement week 52 will be classified as not achieved remission.
- Proportion of subjects experienced Durable Remission (CDAI score < 150) from week 26 through week 52. Subjects experiencing a CDAI score ≥ 150 at any visit time point assessment between week 26 and week 52 or have no CDAI measurement week 26 or week 52 will be considered not achieved Durable Remission.
- Proportion of subjects in Early Remission week 16, where remission is defined as a subject having a CDAI score of < 150 . Subjects who have a week 16 CDAI score ≥ 150 or who do not have a CDAI measurement week 16 will be classified as not achieved early remission.
- Proportion of subjects in steroid free remission week 52, where remission is defined as a subject having a CDAI score of < 150 . Subjects must be maintained off steroids for 3 weeks in order to be determined to be in steroid free remission, e.g., by week 49.

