6.1.2 Multiplicity and Testing Strategy

Multiplicity issues in statistical inference in this study may arise from repeated tests on several multiple endpoints specified in the protocol. Additionally, the impact of the Type I error probability (α) because of the formal planned interim analysis to be conducted needs to be understood.

The protocol specified α -spending for the planned interim analysis is 0.003. Hypotheses tests at the final analysis will be conducted at significance level of $\alpha = 0.049$. The multiple efficacy tests for the study final analysis will employ a serial sequential gatekeeper strategy to maintain the Type 1 error rate at $\alpha = 0.049$ across two families of analyses that support the primary, and key secondary objectives. The protocol pre-specified strategy is to use a hierarchy of significance tests where each test acts as a gatekeeper to tests below it. The endpoints will be tested in a sequential manner and will follow the sequential order given below starting with Remission ranked 1. Any inferential and hypothesis testing of a subsequent endpoint will be performed only if the test for the preceding endpoint is significant. In other words, the endpoint hypothesis examined earlier serves as gatekeeper. For this study as listed below in sequence of clinical importance, Remission week 26 is first rank (1) and will be tested first followed by Response week 26 (rank 2), followed by Remission week 52 (rank 3), Durable Remission week 26 through week 52 (rank 4), followed by Remission week 16 (rank 5), and followed by Steroid free Remission week 52 (rank 6). Again it is important to note that once one hypothesis is tested and found not to be significant at $\alpha = 0.049$, all subsequent tests will not be performed. The multiplicity adjustment following hierarchal testing procedure comparing RHB-104 with Placebo will only be performed on the following key clinical efficacy endpoints listed in order of clinical importance:

1. Remission (CDAI score < 150) week 26 - Primary Efficacy Endpoint.
Key Secondary Efficacy Endpoints:
2. Response (reduction from baseline of ≥ 100 in CDAI score) week 26.
3. Remission (CDAI score < 150) week 52
4. Durable Remission (CDAI score < 150) from week 26 through week 52 in remission.

5. Remission (CDAI score < 150) week 16
6. Proportion of subjects in steroid free remission week 52 (CDAI score < 150 and no steroids use by week 49).

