6.1.5 Missing Data and Handling of Dropouts

All available efficacy and safety data will be included in data listings and tabulations. All patients who prematurely discontinue for any reason will be considered failures for the different proportion based endpoints.

CDAI Missing Data:

Final Version 3.0, 05 April 2018

The computation of CDAI requires 7 days of consecutive diary daily data. For subjects with CDAI diary data reported that is less than 7 days of data, the reported data will be standardized to 7 days by dividing the sum of CDAI score over the number of days of data by total number of days of reported data multiplied by 7. If less than 4 days of diary data is available, the subject will be categorized as a non-responder and the CDAI score will be considered missing. As specified in the protocol, subjects with missing week 26 assessment will be assumed to not be in a state of remission at week 26 (i.e., non-responders). Similarly, for subjects with missing week 52 assessments will be assumed not to be in state of remission at week 52. Sensitivity analyses may be performed on Observed Case (completer analysis) only.

Handling of missing date information for AEs:

The term *missing date* refers to a completely missing date or to partial date where month or/and day or/and year is/are missing, e.g. missing month/day/year. Missing start and end dates will be imputed conservatively, i.e. missing values will be imputed in such a way that the duration of the AE is considered with the longest possible duration. The missing start date and end date of AE will be imputed for the purpose of defining treatment emergent adverse events (TEAE) and for assigning events to treatment periods using the following definitions:

(i) Adverse Event Start Date:

Event Missing Day: If Adverse event day is missing but month and year present, then impute the 1st of the month unless month and year are the same as first dose of study drug then impute day first day of dose.

Event Missing day and month – If adverse event day and month both are missing but year is present then impute 1st January unless year is the same as first dose date then impute day and month first dose day and month.

Completely missing – impute first dose date unless the end date suggests it could have started prior to this in which case impute the 1st January of the same year as the end date.

(ii) Adverse Event End Date:

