6.7 Interim Analysis

One prospectively planned interim analysis for safety and futility is planned after 50% (205) patients have completed week 26 of treatment. The DSMB will evaluate the results from this analysis to assess RHB-104 safety, efficacy (or inefficacy), and the feasibility of continuing or stopping the study. The planned interim analysis is designed to have an alpha level of 0.003 as the criteria for stopping the trial early for efficacy or inefficacy based on using the O'Brien-Fleming spending function to determine the test boundaries. For the interim analysis, the Cochran-Mantel-Haenszel (CMH) test will be used to compare treatment groups controlling for the

Final Version 3.0, 05 April 2018

stratification variable (anti-TNF agents (yes/no). The interim test is a 2-sided test ($P=0.003$), meaning that the trial can be stopped if there is overwhelming evidence of efficacy or overwhelming evidence of inefficacy. Further details are provided in the DSMB charter for this study.

The protocol specified α -spending for the prospectively plan interim analysis is 0.003. All tests at the final analysis will be conducted at significance level of $\alpha = 0.049$. The interim analyses will consider subjects with missing 26 week assessments to not be in a state of remission at 26 weeks.

Regarding the interim efficacy (or inefficacy) of the data, recommendations for early termination will be guided by the Lan-DeMets alpha-spending implementation of O'Brien-Fleming spending function to determine the test boundaries. The efficacy boundary preserves the overall 2-sided study alpha level of 0.05. The alpha level at first & second sequential test is 0.003 & 0.049, respectively.

The DSMB will carefully consider the safety and efficacy interim results and then provide a recommendation for continuing or stopping the study. The sponsor and all personnel involved in the conduct of the study will remain blinded to the treatment assigned to each subject. The DSMB will disseminate interim results in a manner that will protect the scientific and ethical aspects of the study. The responsibility of the DSMB, the scope of the data to be reviewed, the organization of the review process, dissemination requirements and procedures are described in DSMB charter.

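### As worded, the Week 26 trigger, the single ranked sequence and the missing-as-failure rule would score patients not yet due at Week 52 as failures in three key secondary tests

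*SAP*

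**What the plan says.** Timing. SAP 6.1.9 and the Version 11.0 paragraph of the protocol's Statistical Considerations carry the same sentence: "Final analysis of the data is to be carried out when approximately 324 patients have completed the Week 26 primary endpoint assessment". The figure of 324 is also the whole curtailed enrolment. Earlier in the same SAP section, "the final analysis (second sequential test) will be performed using a 2-sided alpha level of 0.049 for testing the primary outcome".

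Content of the final analysis. SAP 6.1.2: "The multiple efficacy tests for the study final analysis will employ a serial sequential gatekeeper strategy". The order is remission at Week 26, then response at Week 26, "followed by Remission week 52 (rank 3), Durable Remission week 26 through week 52 (rank 4"), then remission at Week 16 (rank 5) and steroid-free remission at Week 52 (rank 6). Testing stops at the first non-significant result. SAP 6.7 adds: "All tests at the final analysis will be conducted at significance level of" 0.049.

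Missing data. For rank 3, SAP 2.2.2 says that subjects "who do not have a CDAI measurement week 52 will be classified as not achieved remission". For rank 4, those who "have no CDAI measurement week 26 or week 52 will be considered not achieved Durable Remission". SAP 6.1.5 gives the general rule, which also covers rank 6: "for subjects with missing week 52 assessments will be assumed not to be in state of remission at week 52". SAP 5 defines the ITT set as everyone randomised.

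**The concern.** When the last of about 324 patients reaches Week 26, anyone randomised less than 52 weeks before the data cut cannot yet have a Week 52 CDAI. Nothing in the supplied text separates such a patient from one who dropped out or missed the visit, so both score as failures.

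The SAP does allow for incomplete follow-up elsewhere. Section 2.2.3.2 censors subjects still on study for time to remission, and 6.3.4.1 schedules repeat analyses for MAP cultures that have not had time to grow. The Week 52 proportions have no matching provision.

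Section 2.2 links the key secondary endpoints to possible labeling claims. Diluted Week 52 rates reduce power at ranks 3, 4 and 6. Because the sequence is strict, a miss at rank 3 or 4 that arises only from pending visits also blocks rank 5, whose Week 16 data would be complete.

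**Working it through.** **Inputs from the documents:** 162 per arm, 36% vs 21% remission and stated power of at least 80% (SAP 6.1.9); two-sided alpha 0.049 (SAP 6.1.2, 6.3.1).

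**Assumptions, because the documents give no figure:** uniform accrual over 3 to 4 years (156 to 208 weeks); Week 52 rates equal to the Week 26 design rates; delay from trigger to data cut of 0, 8 or 12 weeks. An unstratified two-proportion test stands in for the CMH test.

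**Step 1. Reproduce the plan's power.** Power = Φ[(d − z·SE0)/SE1], with SE0 pooled and SE1 unpooled. Here d = 0.15, z = 1.9686, SE0 = √(2 × 0.285 × 0.715/162) = 0.05016 and SE1 = √((0.21 × 0.79 + 0.36 × 0.64)/162) = 0.04946. Power = Φ[(0.15 − 0.0987)/0.0495] = 85.0%, or 81.9% with a continuity correction. Both agree with the stated figure, so the sample size is not at fault.

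**Step 2. Share not yet due.** For accrual over A weeks and a delay of D weeks, f = (26 − D)/A. With D = 0, f = 26/156 = 16.7% (54 of 324) or 26/208 = 12.5% (about 40 of 324).

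**Step 3. Effect on rank 3.** Scoring pending patients as failures multiplies both rates by (1 − f) and keeps 162 per arm. Expected false failures with no delay are 162 × f × (0.36 + 0.21), which is 15.4 at 3 years and 11.5 at 4 years.

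| Accrual | Delay (weeks) | Not due | Rates | Difference (points) | Rank 3 power |
|---|---|---|---|---|---|
| All followed to Week 52 | n/a | 0% | 36.0% vs 21.0% | 15.0 | 85.0% |
| 3 years | 0 | 16.7% | 30.0% vs 17.5% | 12.5 | 75.3% |
| 3 years | 8 | 11.5% | 31.8% vs 18.6% | 13.3 | 78.6% |
| 3 years | 12 | 9.0% | 32.8% vs 19.1% | 13.7 | 80.1% |
| 4 years | 0 | 12.5% | 31.5% vs 18.4% | 13.1 | 78.0% |
| 4 years | 8 | 8.7% | 32.9% vs 19.2% | 13.7 | 80.3% |
| 4 years | 12 | 6.7% | 33.6% vs 19.6% | 14.0 | 81.4% |

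With no delay, the outer range is 69.4% at 2 years (f = 25%) and 80.5% at 6 years (f = 8.3%).

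**Step 4. Type I error.** Equal rates multiplied by the same (1 − f) stay equal, and blocked 1:1 randomisation keeps the pending share similar in the two arms. The exact two-sided error, with both arms at 21% or both at 36% and f from 0 to 25%, is 0.0487 to 0.0497. Those values include f = 0, so pending visits do not inflate it.

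**The case against.** A reader might infer that the plan schedules the Week 52 tests on a Week 26 data cut. No sentence says so. The trigger sits in the sample-size section, names the primary endpoint assessment, and is followed by a power statement for that endpoint alone. Section 6.1.9 describes the second sequential test as one of the primary outcome, 6.1.2 gives no date for the study's final analysis, and 6.7 sets an alpha without naming the ranks. The narrower reading, in which the trigger times only the primary test, is therefore open. It leaves ranks 3 to 6 without any stated timing in the supplied text.

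A reader might also infer from SAP 6.3.4.1 that there is only one lock. That section mentions a data lock without dating it and then describes later analyses, so it does not settle the matter. Disposition in 6.2.1 counts Week 52 completers, which suggests that full follow-up is expected. The rule in 6.1.5 stands under a heading on missing data and dropouts, where a visit not yet due fits poorly. However, the wording in 2.2.2 turns only on having no measurement, and it is broad enough to include such visits.

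Two limits stand. The protocol body and the SAP addendum named in 6.3 were not supplied and could contain a timing rule. The size also depends on unstated inputs: a delay before the data cut, or slower accrual at the end, shrinks the loss.

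**Conclusion.** The concern holds as a conflict between stated rules: taken together as written, they score patients not yet due as failures at ranks 3, 4 and 6. It does not show that the sponsor intends this. On either reading the supplied text lacks a sentence that it needs.

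Under the stated assumptions, the loss of rank 3 power is about 7 to 10 percentage points if data are cut at the trigger (85% to 75-78%), and about 4 to 6 points if the cut comes 8 to 12 weeks later (85% to 79-81%). These figures are illustrations, not estimates for this trial. The error is conservative. It leaves the primary test and Week 26 response untouched and is confined to the key secondary claims, including rank 5 through the gate. It should be fixed before unblinding. Confidence is medium because of the unsupplied documents.

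**What to change.** Before unblinding, make the same change in SAP 6.1.2, SAP 6.1.9 and the protocol's Version 11.0 text:

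- The Week 26 trigger times ranks 1 and 2 only.
- Ranks 3 to 6 are tested in the stated order, each at 0.049 and only if every earlier rank is significant, after every randomised subject has completed Week 52 or discontinued. Transfer to RHB-104-04 counts as discontinuation for this purpose.
- The text names who stays blinded between the two locks, since some patients will still be on double-blind treatment.

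As a safeguard, state in 2.2.2 and 6.1.5 that a missing Week 52 CDAI counts as failure when the visit was due or the subject had discontinued.

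The cost is a few sentences, a second database lock, and key secondary results (including rank 5, which keeps its place in the order) up to about 26 weeks after the primary result. No extra patients or visits are needed, and the test order and alpha do not change.

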6.2 Subject Characteristics

All subject characteristics data will be listed by subject, and summarized for the ITT and safety populations, except as noted otherwise.

6.2.1 Subject Disposition

Subject disposition will be presented for all subjects by treatment group and overall for the Enrolled, randomized, ITT and SAF populations. Disposition information that will be summarized will include number of subjects who completed the study, number who withdrew prematurely, and reasons for withdrawal.

All screened subjects will be summarized in subject disposition summary tables. The number and percent of screened subjects in each of the following categories will be presented.

- Subjects screened
- Screen failures and by criteria
- Subjects randomized
- Subjects completing weeks 26 and 52
- Subjects discontinued from the study and by reason of discontinuation.

The number and percentage of randomized patients who are ITT evaluable, mITT evaluable, safety evaluable (SAF), and PP evaluable will be summarized by treatment group and overall.

The number and percentage of randomized subjects, who complete the study through weeks 26, and 52, and who discontinue the study by reason will be summarized by treatment group and overall.

6.2.2 Protocol Deviations

Subjects with major protocol deviations will be identified by the medical or clinical data review prior to database lock. The deviations will be summarized by treatment group and overall based on the safety population and ITT population. The summary will be grouped into different categories of violations such as:

- Errors in treatment assignment
- Violation of inclusion/exclusion criteria
- Non-compliance with study procedures
- Inappropriate intake of prohibited medications
- Poor compliance with study medications
- Lost to follow-up
- Administrative decision of investigator or sponsor

Multiple deviations can occur in the same subject and thus a subject may be counted in more than one deviation category.

A listing of subjects with major deviations will be presented.

All decisions regarding major deviations will be discussed and agreed upon with the sponsor prior

Final Version 3.0, 05 April 2018

to the database lock.

6.2.3 Demographics and Background Baseline Characteristics

6.2.3.1 Subject Demographics data.

Demographics data is collected at time of screening after informed consent is obtained. Demographics variables will be summarized descriptively for the ITT and SAF population by treatment group and will include the following variables:

- Age at enrollment continuous variable [Years]
- Sex
- Race
- Ethnicity
- Height
- Weight
- BMI

6.2.3.2 Background/Baseline Characteristics

The following list of variables will be summarized to further characterize the patient population at baseline by treatment group:

- Crohn's disease (CD) characteristics: CD Surgical history; duration of CD since first diagnosis, baseline CDAI score; baseline CDEIS and SES-CD scores
- Age at first diagnosis
- Stratification anti-TNF agents (yes or no)
- Smoking
- Alcohol consumption
- MAP Test status: PCR Blood Assay: (Positive/Negative) Baseline
- Map Test status: Blood Culture (Positive/Negative) Baseline
- Baseline serum inflammation marker: C-reactive protein (CRP)
- Baseline stool inflammation marker: Fecal calprotectin
- Baseline IBDQ
- Prior use of steroids (yes/no)
- Prior use of immunomodulators (yes/no)

The final analysis list of baseline characteristics will be completed at the time of analysis depending on the available data. The baseline characteristics will be summarized descriptively for the ITT population by treatment group. Continuous data summary descriptive statistics will include the number of observations, means, standard deviations, medians, and ranges. Categorical variables will be summarized with frequencies and percentages.

